2.2 Current standard therapy of classical HL: Based on several randomized studies comparing ABVD (doxorubicin, bleomycin, vinblastine, and dacarbazine) with other multi-drug regimens, ABVD became the most widely used combination regimen for the treatment of patients with advanced HL.[2-4] Chemotherapy alone (6-8 cycles) is usually considered to be sufficient for the treatment of patients with advanced stage classical HL. However, involved field radiation therapy is frequently added at the end of chemotherapy to areas of bulky disease. This combined modality approach has been recently compared to chemotherapy (MOPP/ABV) alone in a randomized trial in patients with advanced stage classical HL, and showed no survival advantage, especially in those who achieved complete remission after the completion of chemotherapy.[5] Furthermore, meta-analysis review of fourteen clinical trials comparing chemotherapy with combined modality also showed no survival advantage for those receiving the combined modality approach.[6] Newer treatment programs such as Stanford-V and BEACOPP have shown successful results, but remain less widely used compared with ABVD.[7-9] Although BEACOPP has been shown to be superior to ABVD-like regimens in large scale randomized trials, the superiority of Stanford-V over standard ABVD has not yet been established.[10] Because ABVD may cure only 50-65% of patients with poor risk advanced stage HL, more intensive programs such as BEACOPP may add benefit, despite the increased toxicity. Patients with good risk features have a high cure rate with ABVD, so the use of more intensive and more toxic regimens in this patient population should be used with caution, and preferably within a clinical trial.

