2.3 The International Prognostic Index (IPS): HL is staged according to the Cotswold modification of the Ann Arbor staging system.[12] Only imaging studies and bone marrow biopsies (clinical staging) are used for stage assignment and treatment planning. The international prognostic score (IPS) was developed to further guide therapy of patients with advanced stage HL.[11] In this model, seven factors are used [Table 1]. Using this model, 42% of patients with advanced stage HL are expected to have an IPS score of >2 (3-7), and those patients are expected to have a 55% 5-year freedom from progression with ABVD-like therapy. In contrast, patients with IPS score 0-2 are expected to have 74% 5-year freedom from progression. Thus, patients with IPS score of > 2 have a poor outcome with current standard therapy, and will be included in this proposed study.

Table 1	
International Prognostic Score (IPS) for Advanced HL[11]	
1. Sex :	male
2. Age:	≥ 45
3. Stage:	IV
4. Hemoglobin	<10.5 g/dl
5. WBC:	≥ 15,000/
6. Lymphocyte count	< 600/ or < 8% of WBC
7. Serum albumin	< 4 g/dl

2.4 Rational for using rituximab for the treatment of classical HL:

2.4.1 Role of reactive B-cells in the microenvironment: HRS cells are surrounded by an overwhelming number of reactive cellular infiltrate. These reactive cells are not bystander cells, as once thought of. In contrast, they frequently provide survival signals to HRS cells.[13] The role of the microenvironment in supporting the survival and growth of HRS cells is best illustrated by the difficulty of establishing HRS-derived cell lines. Once HRS cells are taken out of the microenvironment, it is extremely difficult to grow them in culture. It is, therefore, ironic that the host own immune cells are providing survival factors to the malignant cells, creating an “immune-betrayal” phenomenon. Therefore, we hypothesized that eliminating these reactive cells from the microenvironment may deprive HRS cells from critical survival factors and may lead to their growth arrest and death.[13]

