2.5 Results with rituximab plus ABVD: The clinical activity of rituximab in patients with relapsed classical HL (irrespective of CD20 expression by HRS cells) was recently examined by our group at M. D. Anderson Cancer Center, in which rituximab was used to deplete CD20+ reactive B lymphocytes from HL microenvironment.[15] Twenty-two heavily pretreated patients with classical HL were treated with six weekly doses of rituximab. Five (22%) patients achieved partial or complete remissions, and eight additional patients had stable disease. Clinical remissions were observed in patients irrespective of CD20 expression by HRS cells, but were observed in patients whose disease was confined to the lymph nodes. In a follow-up study, we combined rituximab with ABVD (R-ABVD) chemotherapy to treat patients with newly diagnosed classical HL.[16, 17] In this phase II study, 65 patients with classical HL were treated with R-ABVD. With a median follow up of 32 months, the estimated event-free survival (EFS) is 82% and overall survival 100%. Importantly, the EFS was improved for all risk categories: for patients with a prognostic score of 0-1 the EFS was 92%, for score 0-2 was 86%, and for score 3-5 was 73% (Fig 1, Table 2).

Table -2 : Event free survival (EFS) observed in patients treated with R-ABVD compared to historical data with ABVD alone. EFS is shown in different groups according to IPS.

IPS Group	ABVD 3-year EFS	R-ABVD 3-year EFS
0-1	79%	95%
0-2	74%	87%
2	67%	76%
>1	60%	76.5%
>2	55%	77%
>3	47%	71%

[figure not shown]

Figure 1: Event free survival (EFS) in 65 patients treated with rituximab plus ABVD (R-ABVD); (Left) results are shown in 5 risk groups according to the international prognostic score (IPS). (Right) results are shown in patients with IPS score of 0-2 and > 2. The same data is shown in Table 2.

2.6: Role of early PET imaging in predicting treatment outcome: While the IPS may predict treatment outcome in patients with advanced HL, others have recently examined

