According to the historical data, the three-year EFS rate is 55% for the patients treated with ABVD and 77% for the patients treated with R-ABVD. A 22% improvement in three-year EFS rate is considered a clinically significant outcome for the groups. The corresponding hazard ratio between the R-ABVD group and the ABVD group is 0.437 based on the assumption that the time to event follows an exponential distribution. Assuming two-sided type I error rate of 0.05, accrual rate of 3 patients per month, and additional 39 months of follow-up, a trial with 54 patients each arm will have 80% of power to detect a 22% improvement in three-year EFS rate. Two interim analyses will be performed to allow for the early termination of the trial in light of evidence that one treatment arm is superior to the other treatment arm or there is no difference between the two treatment arms. In order to provide an overall significance level of 0.05 for the study, the interim analyses will use a Lan-DeMets monitoring boundary with an O'Brien-Fleming stopping rule (Cytel 2004). The interim analyses will be performed when 17 and 35 out of the expected 52 events have been observed. Using O'Brien-Fleming outer test boundaries, the two-sided Z-score test cut-offs at the two interims and final analyses for rejecting the null hypothesis will be ± 3.71 , 2.51, and 1.96, respectively. The inner (futility) Z-score boundaries for stopping and accepting the null are 0.04, 0.95, and 1.96. By factoring in the 10% of patient drop-out rate, the total number of patients will be enrolled to the study is 120.

Analysis Plans

Patients' demographic information at baseline will be analyzed, with data summarized in tables listing the number of subjects per treatment group in order to assess comparability. The student t-test or the Wilcoxon test will be used to compare continuous variables between two different patient groups. The chi-square test or the Fisher's exact test will be applied to assess the association between two categorical variables. Logistic regression will be utilized to assess the effect of patient prognostic factors on the response rate.

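### Section 11 counts on exponential events after year 3 that the protocol's own 5-year and cure figures do not support, so 52 events and 80% power look optimistic, and the 55% control rate carries two time points

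*Combined protocol and SAP*

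**What the plan says.** Section 11.0 (Sample Size and Power) states that "the three-year EFS rate is 55% for the patients treated with ABVD and 77% for the patients treated with R-ABVD". It assumes exponential event times, derives a hazard ratio of 0.437, and gives 80% power for 54 patients per arm at two-sided 0.05, with accrual of 3 per month and 39 further months of follow-up. Looks are set at 17 and 35 of 52 expected events, with a Lan-DeMets O'Brien-Fleming boundary. Enrolment is raised to 120 for 10% dropout.

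The background sections give these figures:

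- Section 2.3, for IPS >2: "those patients are expected to have a 55% 5-year freedom from progression with ABVD-like therapy". For the better-risk group: "patients with IPS score 0-2 are expected to have 74% 5-year freedom from progression".
- Section 2.5, Table 2, lists the same 55% (IPS >2) and 74% (IPS 0-2) under the column head "ABVD 3-year EFS".
- Section 2.2: "Because ABVD may cure only 50-65% of patients with poor risk advanced stage HL", more intensive programmes may add benefit.
- Section 2.5 text, for R-ABVD: "for score 0-2 was 86%, and for score 3-5 was 73% (Fig 1, Table 2"). Table 2 shows 87% for 0-2 and 77% for >2, and the Figure 1 legend says "The same data is shown in Table 2".

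**The concern.** Two things do not fit together. First, 55% appears for the same risk group as a 3-year EFS rate and as a 5-year freedom-from-progression rate. Both can be true only if almost nothing happens between years 3 and 5. Second, an exponential curve has no plateau and no cured patients, yet Section 11 uses one to project events over 39 to 75 months of follow-up in a disease where the protocol expects at least half of these patients to be cured on the control arm.

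The 52 events fix the timing of the looks, the final analysis and the power claim for the primary endpoint. If fewer events occur, a non-significant result would be read against power the trial does not have, and the second look would fall much nearer the end of the information than planned. Further follow-up would add little if the curves are flat.

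**Working it through.** **1. The plan's own figures reproduce.**

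- HR = ln 0.77 / ln 0.55 = 0.437.
- Freedman events = (1.960 + 0.842)² × (1.437 / 0.563)² ≈ 51.2, rounded up to 52.
- Expected events per arm = n × [1 − (e^(−39λ) − e^(−75λ)) / (36λ)], with λ = −ln S(36) / 36 and 108 patients entered over 36 months. ABVD: λ = 0.0166, 32.7 events. R-ABVD: λ = 0.00726, 18.2 events. Total 50.9.
- Freedman power at 50.9 events = Φ(√50.9 × 0.563/1.437 − 1.96) = 79.8%.
- 108 / 0.90 = 120.

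**2. What the exponential implies later.** ABVD EFS at 5 years = 0.55^(5/3) = 36.9%, against 55% in Section 2.3. By year 3 the plan expects 54 × (0.45 + 0.23) = 36.7 events. The other 50.9 − 36.7 = 14.2 (28%) come from the tail.

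**3. Check against the cure figure.** If 50% of ABVD patients are cured (the lowest value in Section 2.2) and cured patients have no EFS event, the ABVD arm can yield at most 54 × 0.50 = 27.0 expected events however long follow-up lasts. The plan projects 32.7. At HR 0.437 the R-ABVD plateau is 0.50^0.437 = 0.739, which gives 54 × 0.261 = 14.1. The cap for both arms is 41.1 (with 60 per arm, 30.0 + 15.7 = 45.7).

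**4. Events and power with 55%/77% at 3 years and HR 0.437 kept.** Two tails were used.

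- Flat after year 3: n × 0.68, so 54 per arm gives 36.7 and 60 per arm gives 40.8.
- 50% cured: S(t) = exp[ln 0.5 × (1 − e^(−t/m))] with S(36) = 0.55. Then e^(−36/m) = 1 − 0.8625 = 0.1375 and m = 18.1 months. S(60) = 0.51. Events are 26.0 + 13.5 = 39.5 (54 per arm) and 29.0 + 15.0 = 44.0 (60 per arm).

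Power was taken from the Freedman formula and from simulated log-rank tests with the stated bounds, with and without the futility bounds (6,000 to 20,000 trials per case, standard error at most about 0.6 points). Where 52 events were not reached, the simulated final test was made at 1.96, 39 months after last entry. Dropout, where included, is 10% by 36 months.

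| Tail | Patients | Events | Freedman | Simulated |
|---|---|---|---|---|
| Exponential (plan) | 108 | 50.9 | 80% | 80-83% |
| Flat after year 3 | 108 | 36.7 | 66% | about 69% |
| Flat after year 3 | 120, 10% dropout | 39 | 69% | 70-73% |
| Flat after year 3 | 120, no loss | 40.8 | 71% | up to 74% |
| 50% cured | 108 | 39.5 | 69% | about 72% |
| 50% cured | 120, 10% dropout | 42 | 72% | 74-75% |
| 50% cured | 120, no loss | 44.0 | 74% | up to 78% |

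A milder tail, with the later hazard a quarter of the earlier one, gives 50% at 5 years, 41-46 events and about 73-78% power.

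**5. Effect on the looks.** 35/52 = 67% as planned. With flat curves it is 35/40.8 = 86% to 35/36.7 = 95% of expected events, and 35 events are not reached in 10% (120 patients, no loss) to 32% (108) of trials. With 50% cured it is 35/44.0 = 80% to 35/39.5 = 89%.

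**6. If the 55% is a 5-year rate.** The 3-year control rate then lies between 55% (flat from year 3) and 0.55^(3/5) = 70% (constant hazard to year 5). The hazard ratio against 77% lies between 0.437 and ln 0.77 / ln 0.70 = 0.73. The documents do not say where.

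**The case against.** The strongest reply is that Section 11 contains no calculation error and agrees with Table 2 in both endpoint and time point. That stands: the issue is the label on an input and the shape of the tail.

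EFS is also not freedom from progression. The documents list no events for EFS, Section 10 treats non-responders as failures, and deaths or changes of therapy may count. EFS could therefore run lower by an unknown amount, and the cure range in Section 2.2 is a background remark, not a curve. This limits how firmly the power loss can be stated. It does not supply support for a fall from 55% to 37% between years 3 and 5.

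A curve fully flat from year 3 is the extreme case, which is why the 50%-cured and quarter-hazard cases are shown beside it. All of them stay below 52 expected events.

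A Lan-DeMets boundary adapts to the actual event count. True, and type I error is not at issue. Power is.

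Two stronger readings are tempting. Because both 55% and 74% recur under two time points, a reader might infer that 5-year rates were copied into a 3-year column. That is plausible but not shown: the historical source is not in the documents, and both 55% figures hold if the curve is flat. A reader might also put power near 50% or lower. Such values come from moving the control's 3-year rate above 55% through a curve shape that the documents do not contain, which changes the effect size and not only the event count.

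**Conclusion.** The concern holds in limited form and should be fixed. The 55% carries two time points and two endpoints, and the exponential tail behind about 14 of 51 expected events is not supported by the protocol's own figures unless EFS runs well below freedom from progression.

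With the stated 3-year rates kept, expected events are about 37-44 instead of 52, and power is about 69-78% instead of 80%. For 120 patients with 10% dropout and flat curves, it is 39 events and 70-73%. These figures assume proportional hazards up to the plateau and no EFS events among cured patients. If the 55% is a 5-year rate, power may be lower still by an amount the documents do not settle.

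Confidence is high that the passages disagree and moderate on the size of the loss. The R-ABVD figures (73% in the text, 77% in Table 2) are a separate, smaller discrepancy: the 73% has no stated time point and its group is labelled 3-5, not >2.

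**What to change.** - In Sections 2.3, 2.5 and 11, state one endpoint and one time point for the 55%, with its source, and reconcile 73% with 77% for R-ABVD.
- In Section 11, recalculate expected events and power for the fixed 120 patients, including the 10% dropout, under a plateau or cure model consistent with Sections 2.2 and 2.3. Replace the 52 expected events and the 80% with that range, and show the exponential case as its optimistic end. If the 55% is confirmed as 3-year EFS, the figures above are a starting point. If it proves to be a 5-year rate, derive the 3-year control rate and hazard ratio again first.
- Restate the 17- and 35-event looks as shares of the new total.
- Add a sentence such as: *If 52 EFS events are not reached, the critical value of the final analysis is recalculated from the Lan-DeMets O'Brien-Fleming spending function at the actual event count.* Do not cap the final analysis at 39 months: Section 11 uses 39 months as a sizing assumption, and Section 8.0 continues yearly follow-up, which could add events if the curves are not flat.

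The cost is recalculation and wording; no patients are added. Recalculating the critical value (1.96-1.97 at 37-41 events, futility bounds ignored) moves power by under 1 point. The downside is a less favourable stated power, which restating does not bring back to 80%.

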11. STATISTICAL CONSIDERATION
12. REPORTING REQUIREMENT
13. REFERENCES
14. APPENDIX

INFORMED CONSENT

Study Chairman: [name].

Collaborators:

~~[name]~~, M.D.

~~[name]~~, M.D.

~~[name]~~, M.D.

~~[name]~~, M.D.

~~[name]~~, M.D.

~~[name]~~, M.D.

~~[name]~~, M.D., Ph.D.

~~[name]~~, Ph.D.

1.0 OBJECTIVES:

1.1 Primary:

To evaluate the event free survival (EFS) following therapy with rituximab plus ABVD or standard ABVD in patients with newly diagnosed classical Hodgkin lymphoma who have poor prognosis defined as International prognostic score (IPS) of > 2.

1.2 Secondary:

1.2.1 To compare the effect of the two treatment arms on PET scan results after 2 cycles of therapy

1.2.2 To compare the effect of the two treatment arms on the level of circulating malignant Hodgkin stem cells

2.0 BACKGROUND:

2.1 Hodgkin lymphoma: The world health organization (WHO) classification of Hodgkin lymphoma (HL) distinguished between two major subtypes, classical HL and nodular lymphocyte predominant HL.[1] Approximately 95% of patients with HL will have the classical HL histology, which is characterized by the presence of rare malignant Hodgkin and Reed Sternberg (HRS) cells among an overwhelming number of benign reactive cells. In recent years, new studies shed more light on the biologic and molecular features of HRS cells providing hopes that new targeted therapy may be developed to enhance the cure rate and to reduce treatment-related toxicity.

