the prognostic role of PET imaging after starting therapy. Using this approach, Hutchings and colleagues prospectively assessed the value of positron emission tomography with 2-[18F]fluoro-2-deoxy-D-glucose (FDG-PET) after two cycles of chemotherapy for prediction of progression-free survival (PFS) and overall survival (OS) in Hodgkin lymphoma (HL).[18] Seventy-seven consecutive, newly diagnosed patients underwent FDG-PET at staging, after two and four cycles of chemotherapy, and after completion of chemotherapy. After two cycles of chemotherapy, 61 patients had negative FDG-PET scans and 16 patients had positive scans. Eleven of 16 FDG-PET-positive patients progressed and 2 died. Three of 61 FDG-PET-negative patients progressed; all were alive at latest follow-up. Survival analyses showed strong associations between early FDG-PET after two cycles and PFS ($P < .001$) and OS ($P < .01$). Thus, a positive early interim FDG-PET is highly predictive of progression in patients with advanced-stage HL.

- 2.7 **Proposal:** based on the encouraging phase-II data from MDACC, we propose to confirm these results in a randomized study focusing on patients with poor risk features (IPS score > 2). Furthermore, we will compare the effect of these two treatment arms on PET imaging after 2 cycles of therapy, and on the level of circulating HL stem cells, and correlate these results with EFS.

3.0 DRUG INFORMATION:

Rituximab

Rituximab is a genetically engineered, chimeric, murine/human monoclonal antibody directed against the CD20 antigen found on the surface of normal and malignant pre-B and mature B cells. The antibody is an IgG₁ κ immunoglobulin containing murine light- and heavy-chain variable region sequences and human constant region sequences. Rituximab is composed of two heavy chains of 451 amino acids and two light chains of 213 amino acids (based on cDNA analysis) and has an approximate molecular mass of 145 kD. Rituximab has a binding affinity for the CD20 antigen of ~ 8.0 nM.

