Description: DTIC-Dome Sterile (dacarbazine) is a colorless to an ivory colored solid which is light sensitive. Each vial contains 100 mg of dacarbazine, or 200 mg of dacarbazine (the active ingredient), anhydrous citric acid and mannitol. DTIC-Dome is reconstituted and administered intravenously (pH 3-4). DTIC-Dome is an anticancer agent.

Clinical Pharmacology: In a patient with renal and hepatic dysfunction, the half-lives were lengthened to 55 minutes and 7.2 hours. Although the exact mechanism of action of DTIC-Dome is not known, three hypotheses have been offered:

1. inhibition of DNA synthesis by acting as a purine analog
2. action as an alkylating agent
3. Interaction with SH groups

Indications and Usage: DTIC-Dome is indicated in the treatment of metastatic malignant melanoma. In addition, DTIC-Dome is also indicated for Hodgkin's disease as a secondary-line therapy when used in combination with other effective agents.

Contraindications: DTIC-Dome is contraindicated in patients who have demonstrated a hypersensitivity to it in the past.

Warnings: Hemopoietic depression is the most common toxicity with DTIC-Dome and involves primarily the leukocytes and platelets, although, anemia may sometimes occur.

Leukopenia and thrombocytopenia may be severe enough to cause death. The possible bone marrow depression requires careful monitoring of white blood cells, red blood cells, and platelet levels. Hemopoietic toxicity may warrant temporary suspension or cessation of therapy with DTIC-Dome. Hepatic toxicity accompanied by hepatic vein thrombosis and hepatocellular necrosis resulting in death, has been reported. The incidence of such reactions has been low; approximately 0.01% of patients treated.

4.0 PATIENT ELIGIBILITY:

Inclusion Criteria:

- a. Previously untreated patient with classical Hodgkin's lymphoma patients with stage III and IV.
- b. International Prognostic Score of > 2 (patient must have > 2 of the following risk features: Male, ≥ 45 years of age, Stage IV, Albumin < 4 , WBC ≥ 15 , Lymphocytes $< 8\%$ or < 600 , Hgb < 10.5)
- c. Must sign a consent form
- d. Must be older than 16 years
- e. Must have adequate bone marrow reserve (ANC $\geq 1,500/uL$, Platelet $> 100,000/uL$)
- f. LVEF $\geq 50\%$ by MUGA scan or echocardiogram
- g. Serum creatinine < 2 mg/dl, serum bilirubin < 2 mg/dl, AST or ALT $< 2x$ ULN
- h. Bi-dimensionally measurable disease

Exclusion Criteria:

- a. Lymphocyte Predominant Hodgkin's Lymphoma

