5.9 Data Collection and multi-center procedure

Data will be collected on uniform CRFs provided by MDACC. These are to be completed for baseline information and throughout the study as required by the protocol and faxed within 4 weeks after completion of each cycle to:

[name]

Ph:[contact]

[contact]

After patients have completed therapy, completed CRFs will be faxed within 1 month of patient's follow-up visit.

5.10

MDACC's data monitoring committee will review the study. Quarterly conference calls among Principal Investigators and support staff will take place to review enrollment and any safety issues concerning protocol, and to discuss the need for any protocol amendments.

6.0 PRETREATMENT EVALUATION (within 4 weeks of starting treatment):

- 6.1 History and physical examination
- 6.2 Determine IPS score. (Only patients with IPS score of 2 or higher are eligible)
- 6.3 CBC, with differential count and platelet count.
- 6.4 Serum Chemistries: glucose, BUN, creatinine, uric acid, total bilirubin, alkaline phosphatase, LDH, total protein, albumin, SGOT(AST), SGPT (ALT), and calcium.
- 6.5 Immunology: Hepatitis B and C will be tested in all patients.
- 6.6 Appropriate imaging studies which should include at least a chest x-ray (CXR), CT scans of the neck, chest, abdomen and pelvis,
- 6.7 PET scan
- 6.8 Measurement of LVEF by MUGA or echocardiogram
- 6.9 Bone marrow biopsy/aspirate
- 6.10 Serum pregnancy tests for women of child bearing age

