Expression of CD19 and CD20 will be measured overtime. The distribution of biomarkers will be examined first by the exploratory data analysis using scatter plot matrix, box plots, BLiP plot (Lee, 1997) and trellis plot, etc. Correlation among continuous biomarkers will be examined by Pearson or Spearman rank correlation coefficients. The association on discrete biomarkers will be tested by chi-square or Fisher's exact test. McNemar's test will be applied to test the change of a single discrete biomarker over time. Repeated measures analysis including mixed effects model will be performed to analyze biomarkers change over time.

Time-to-event outcomes, including event-free survival and overall survival, will be estimated using Kaplan-Meier method. The log-rank test will be performed to test the difference in time-to-event distributions between patient groups. Cox proportional hazards model will be utilized to include multiple covariates in the time-to-event analysis.

Toxicity data will be summarized by frequency tables. The association between the types and severity of toxicity and the treatment groups will be evaluated. No formal statistical testing will be performed on these summary data.

For the efficacy endpoint, intend-to-treat analysis will be applied to the randomized and eligible patients. For the toxicity endpoint, per-treated analysis will be used to include any patient who received the treatment – regardless of the eligibility nor the duration or dose of the treatment received.

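### The efficacy analysis is called intention-to-treat but drops randomised patients judged ineligible, with no all-randomised analysis planned; separately, Section 6.2 contradicts the IPS > 2 entry rule

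*Combined protocol and SAP*

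**What the plan says.** **Analysis set.** The last paragraph of Section 11.0 (Analysis Plans) reads: "For the efficacy endpoint, intend-to-treat analysis will be applied to the randomized and eligible patients". The next sentence takes toxicity in every treated patient, "regardless of the eligibility nor the duration or dose of the treatment received". Because the authors drop the eligibility condition for toxicity and keep it for efficacy, it has to be read as a real restriction on efficacy.

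**Threshold.** Inclusion criterion (b) in Section 4.0 requires "International Prognostic Score of > 2 (patient must have > 2 of the following risk features". The primary objective in Section 1.1 covers patients "who have poor prognosis defined as International prognostic score (IPS) of > 2". Section 2.3 spells the group out as scores 3 to 7, and Section 2.7 uses the same cut. Section 6.2, in the pretreatment work-up, says instead: "Only patients with IPS score of 2 or higher are eligible".

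**Not found.** The available text contains no efficacy analysis of all randomised patients, either primary or sensitivity. It does not say who judges eligibility for the analysis, when, from which data, or whether blind to arm and outcome. The opening pages and Sections 5.1 and 5.2 are not in the text available for this review, so nothing is claimed about eligibility checks before randomisation.

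**The concern.** Intention-to-treat analysis keeps the comparison that randomisation created. Removing patients afterwards can undo that if the chance of removal depends on both arm and outcome, for example if the file of a patient who relapses is examined more closely in one arm than in the other. Section 5.3 and Appendix A have rituximab given at the lead centre and allow ABVD-arm patients to be treated locally, so records reach the trial by different routes in the two arms. This does not show that ineligibility is detected differently, but it is a reason to close the route. At stake is the validity of the primary log-rank test.

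The IPS conflict is a separate defect that touches the same sentence. If eligibility decides who is analysed, the eligibility rule must have one value. A randomised patient with IPS exactly 2 is out under Section 4.0(b) and in under Section 6.2.

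**Working it through.** **1. The plan's own figures reproduce (Section 11.0).**
- HR = ln(0.77)/ln(0.55) = 0.2614/0.5978 = 0.437.
- Events by Freedman's formula, two-sided 5% and 80% power: (1.960 + 0.842)² × (1.437/0.563)² = 7.85 × 6.52 = 51.2, rounded up to 52.
- Enrolment: 108/0.9 = 120. The 10% is for drop-out; there is no separate allowance for ineligible patients.

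The sample size is not in dispute here.

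**2. Bias from exclusion, with no true effect.** Simulated log-rank tests used these settings:
- 120 patients randomised 1:1, accrual over 120/3 = 40 months, then 39 months of follow-up.
- Exponential EFS with 55% at three years in both arms.
- No drop-out and a single test at |Z| > 1.96, with 40,000 trials per scenario.

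The documents give no ineligibility rate, so 10% and 20% are assumed. All-randomised analysis gives 2.5% false R-ABVD wins throughout.

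| Assumed exclusion of ineligible patients | False R-ABVD wins, 10% ineligible | 20% ineligible |
|---|---|---|
| Unrelated to outcome | 2.5% | 2.5% |
| Half detected, but all with an event on R-ABVD (extreme) | 3.3–3.5% | 4.5–4.8% |
| Half detected, but 75% with an event on R-ABVD | 3.0% | 3.3% |
| Half detected, but all with an event on ABVD (mirror case) | 1.9% | 1.2–1.4% |

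Ranges are over repeated runs. In the extreme case the two-sided error is 5.3% and 5.9%, and the apparent HR is 0.97 and 0.93.

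**3. Cost of analysing everyone.** Suppose 10% of patients resemble the IPS 2 row of Table 2 (67% v 76%; HR = ln 0.76/ln 0.67 = 0.2744/0.4005 = 0.685). Blending hazards:

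(0.9 × 0.2614 + 0.1 × 0.2744) / (0.9 × 0.5978 + 0.1 × 0.4005) = 0.2627/0.5781 = 0.454.

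In the same simulation model, power for all-randomised v eligible-only analysis is:
- Ineligible patients resemble IPS 2: 83.7% v 84.0% (10% ineligible) and 78.3% v 79.0% (20%).
- Ineligible patients carry the full 55% v 77% effect: 87.2% v 83.8% and 87.5% v 79.2%.

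With nobody ineligible, this model gives about 88% power and 58 events. Its figures should be compared with each other and not with the plan's 80% and 52.

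**4. IPS 2 patients, kept or excluded.** Here the plan's basis is used: 108 patients, 36 months' accrual, 39 months' follow-up and Freedman power. This gives 50.9 events and 79.8% power. The IPS 2 share is assumed, and kept patients enter by blending three-year rates.

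| Assumed IPS 2 share | Excluded | Kept |
|---|---|---|
| 10% | 0.9 × 50.9 = 45.8 events, HR 0.437, power 75.5% | 56.2% v 76.9%, HR 0.456, 50.3 events, power 75.5% |
| 20% | 0.8 × 50.9 = 40.7 events, HR 0.437, power 70.5% | 57.4% v 76.8%, HR 0.476, 49.6 events, power 70.7% |

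The excluded power at 20% is Φ(√40.7 × 0.563/1.437 − 1.96) = Φ(0.54) = 70.5%. The loss comes from enrolling these patients; the choice of analysis set hardly changes it.

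**The case against.** The restriction is prespecified and matches the IPS > 2 population of the primary objective. The criteria in Section 4.0 are baseline or history items, and Section 6.0 schedules the work-up within four weeks before treatment. Outcome-driven exclusion is therefore not the natural expectation, and exclusion on baseline facts, judged blind, is unbiased. All of this stands. What is missing is a sentence in the plan that limits the judgement to baseline data or blinds it.

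Section 6.2 is the lone outlier against four other places and may be a drafting slip. That also stands; if all enrolment followed Section 4.0(b), no patient is affected. The sentence still sits in the pretreatment checklist and contradicts the inclusion criterion, so the two must be made to agree.

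Two stronger readings are tempting. A reader might infer that the primary result will be biased towards R-ABVD. The documents describe no process that would do this, and the mirror case runs the other way. A reader might also work back from Table 2 that IPS 2 patients would form a large part of an IPS 2-or-higher population, and conclude that the eligible-only set destroys the trial's power. The documents do not state that share. The inference treats rounded EFS rates as exact weighted averages and gives anything from 32% to 50%. It also needs every site to follow Section 6.2 over the inclusion criterion. Even then, the loss is about the same whether these patients are kept or excluded, so it is no evidence against the analysis set.

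**Conclusion.** The point holds in two separate parts.

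**Analysis set.** The set is mislabelled, and exclusion after randomisation is left open without a safeguard or an all-randomised analysis. There is no bias if exclusion is unrelated to outcome. If it is related to both arm and outcome, the bias is modest and can go either way: false R-ABVD wins of about 3.5% or 4.6% in place of 2.5%, under an assumed extreme detection pattern with an assumed 10% or 20% ineligible. An eligibility check before randomisation, if the unavailable sections contain one, would shrink this further.

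**Threshold.** Membership of the primary set is undefined at IPS exactly 2. This is an enrolment conflict of unknown size, possibly zero.

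Both should be fixed. Neither shows that the sample size is wrong or that bias would occur. Confidence is medium, because the size rests on assumed rates and part of the text was unavailable.

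**What to change.** Replace the efficacy sentence in Section 11.0 with wording such as: *The primary efficacy analysis includes all randomised patients in the arm to which they were assigned. An analysis restricted to eligible patients, with eligibility judged blind to arm and outcome and only from data recorded before randomisation, is a sensitivity analysis.*

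Reconcile Sections 4.0(b) and 6.2 so that one IPS threshold governs enrolment, the analysis sets and the sample-size assumptions. Changing the analysis set alone does not resolve this conflict.

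The change is to protocol and SAP wording only. The statistical cost is the slight dilution shown above; power falls by less than one percentage point if 10% or 20% of patients are ineligible and resemble IPS 2 patients, and rises if they carry the full effect.
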